8.5. Safety Oversight

A Data Monitoring Committee (DMC) comprised of independent consultants with appropriate medical expertise will regularly monitor all aspects of patient safety throughout this study. The DMC will be responsible for adjudicating all available data in a blinded fashion (which may include: vital signs, ECGs, clinical laboratory tests, Surgical Site assessments, Neurosensory evaluations, incidence of SAE and TEAE) to assess the safety of each dose level of CA-008 prior to escalating to the next dose level. Details regarding the DMC will be included in the DMC Charter.

8.6. Study Restrictions

In addition to the criteria described in Sections 8.1 and 8.2, the subject must agree to abide by the following study restrictions:

- Subjects will be asked to abstain from consuming more than 1 (women) or 2 drinks (men) per day of alcohol throughout the study.
- Subjects will be asked to abstain from illicit drug use or non-medical use of therapeutic drugs throughout the study.
- Subjects will be asked to abstain from taking prohibited medications described in Section 9.7 throughout the study.

9. TREATMENTS

9.1. Treatment Administration

9.1.1. Study Medication

The proposed doses of CA-008 to be evaluated in this study are:

- CA-008, 0.5 mg in 10 mL of saline (50 µg/mL)
- CA-008, 1.0 mg in 10 mL of saline (100 µg/mL)
- CA-008, 2.0 mg in 10 mL of saline (200 µg/mL)
- CA-008, 3.0 mg in 10 mL of saline (300 µg/mL)
- CA-008, 4.2 mg in 14 mL of saline (300 µg/mL)

In addition, saline for injection, USP will be used.

The study drug is provided as a concentrate that will be diluted just before use in the surgical setting, 1:10 with saline for injection, USP. The study drug will be stored at -20°C (-15°C to -30°C) until the day of surgery. The study drug will be blinded before introduction to surgical setting.

Note: Weights of CA-008 are provided for the free base, without counterions. The drug product uses CA-008 HCl as drug substance, the weights and concentrations of the drug product are shown based on the free base.

9.1.2. Placebo

The placebo will be 10 mL of saline for Cohorts 1-4, and 14 mL of saline for Cohort 5.

The placebo is provided identical to the study drug, and will be “diluted” just before use in the surgical setting, 1:10 with saline for injection, USP. The study drug will be stored at -20°C (-15°C to -30°C) until the day of surgery. The study drug will be blinded before introduction to surgical setting.

9.1.3. Rescue Medications

While in-clinic, subjects will be treated with the prescribed analgesic regimen (oxycodone 5 mg every 2 hours); however, if subjects do not get adequate analgesic relief they will be discontinued from the efficacy portion of the study. At this point, subject's will receive standard of care analgesics (which may or may not include intravenous opioids). Regardless of discontinuation status, subjects will be followed for safety. Discontinuation affects the computation of the analgesic endpoint only. In previous post-operative Day 1 bunionectomy studies, oxycodone 5 mg every 2 hours has provided adequate analgesic relief to >90% of placebo subjects.

Day 1: Hours 0-24

- If needed for management of NPRS score of 4 or higher, oxycodone 5 mg every 2 hours.
- An NPRS should be completed within 15 minutes prior to use of rescue medication.

Day 2: Hours 25-48

- If needed for management of NPRS score of 4 or higher, oxycodone 5 mg every 2 hours.
- Subjects should complete their NPRS within 15 minutes prior to taking rescue medication.

Day 3 - Day 15:

- Over-the-counter standard of care analgesics may be used for management of pain.
- If needed for management of NPRS score of 4 or higher, oxycodone 5 - 15 mg every 4 - 6 hours.
- Subjects should complete their NPRS within 15 minutes prior to taking rescue medication.

Day 15 (post-visit) - Day 29/ET

- Over-the-counter standard of care analgesics may be used for management of pain.

9.2. Identity of Investigational Product(s)

9.2.1. Handling, Storage, and Accountability

All study drug will be transported, received, stored, and handled strictly in accordance with the container or product label, the instructions provided to the research site, and applicable regulations.

All study drug should be stored in a secured area and in accordance with the product labeling and all applicable laws, regulations, and local/institutional requirements. The Drug product will need to be stored at -20°C (-15°C to -30°C) in a freezer. A description of storage conditions for all investigational products will be provided in the Pharmacy Manual.

Detailed drug accountability records must be maintained, including the dates shipments are received, the quantity of material received, the dates dispensed and the running inventory. The unused quantities will be returned to the Sponsor's drug supply vendor at the end of the trial. All unused supplies will be checked against the drug accountability records during the study and/or at the end of the study. The Investigator or designee must maintain an inventory record of all dispensed rescue medications to subjects. Additional details are provided in the Pharmacy Manual.

Mishandling, potential theft, significant loss of clinical supplies, including Investigational Product and Rescue Medication at the site, or other suspected diversion must be reported to the Sponsor or designee within 24 hours of first knowledge of the issue. If diversion is confirmed or suspected (e.g., excessive use of rescue medications), the study staff will be required to complete a clinical supply product complaint form, including documenting if a subject sold drug or gave drug to a friend or relative, if there was a discrepancy in drug accountability and suspected diversion, if a subject had drug stolen, or if there was diversion or theft by site staff or others.

9.2.2. Dispensing and Administration

Only eligible subjects participating in the study will receive the study drug. Only authorized research site staff may supply, prepare or administer the study drugs. Once dispensed, study drug may not be relabeled or reassigned for use by other subjects.

All study drug will be administered by designated blinded healthcare professional(s).

9.3. Method of Assigning Subjects to Treatment Groups

Randomization will be used to avoid bias in the assignment of subjects to treatments, to increase the likelihood that known and unknown subject attributes (e.g., demographics, baseline characteristics) are evenly balanced across treatment groups, and to enhance the validity of statistical comparisons across treatment groups.

Subjects who have provided written informed consent will be assigned a unique number in the screening process. This number will be used to identify the subject throughout the study.

There will be up to 5 cohorts of subjects, each cohort consisting of 8 subjects. Cohorts of subjects will be randomized to either the following active medications or placebo in a 3:1 ratio. The first 4 subjects in cohort one will be dosed initially before the remaining 4 subjects are dosed. Three of these subjects will randomly receive active treatment and 1 will be randomized to placebo. If the safety assessments are acceptable through the first 24 hours, then the second group of 4 subjects will be dosed. Three of these subjects will randomly receive active treatment and 1 will be randomized to placebo.

Once any subject number or randomization number is assigned, it cannot be reassigned to any other subject. This study will use central randomization, as described in Section [10.2](#).

Subjects may be rescreened if the screening window is exceeded due to scheduling issues.

9.4. Selection of Doses

9.4.1. Dose Rationale

In Good Laboratory Practice (GLP) toxicology studies conducted, the NOAEL was identified as 1.5 mg/kg in the rat and 0.25 mg/kg in the dog. The estimation of the maximum safe starting dose for the first-in-human (FIH) study followed the procedure proposed in the FDA Guidance for Industry document “Estimating the Maximum Safety Starting Dose in Initial Clinical Trials for Therapeutics in Adult Healthy Volunteers” (FDA, 2005). Using a conversion factor of 6.2 for rat and 1.8 for dog, the human equivalent dose (HED) is:

- Rat HED = 1.5/6.2 = 0.24 mg/kg
- Dog HED = 0.25/1.8 = 0.14 mg/kg

The most relevant and sensitive species was determined to be the dog (HED = 0.14 mg/kg). Using the recommendation of 1/10th of the HED, a safe starting dose for an FIH would be 0.014 mg/kg. In a 60 kg person, this supports a conservative starting dose of 0.84 mg with a maximum dose of 8.4 mg. The clinical dosing is based on CA-008 and not the salt form. Converting the starting dose to the free base results in a conservative starting dose of 0.77 mg with a maximum dose of 7.7 mg.

As presented in [Table 3](#), Concentric will round down to 0.5 mg as a starting dose and dose escalate to up to 3 mg (cohorts of 0.5, 1, 2, and 3 mg). The 0.5 mg starting dose represents a safety margin from 15.4 at the low dose and the 3 mg maximum dose planned represents a safety margin of 2.6 at the high dose. The rationale to dose escalate to a maximum of 3 mg is based on published clinical data with Capsaicin that demonstrates that this dose should achieve a maximal pharmacologic effect while remaining tolerable. Specifically, studies performed by Anesiva using capsaicin for wound instillation in hernia ([Aasvang et al., 2008 and 2010](#)) and bunionectomy ([Pollak et al., 2009](#)).

Table 3 Human Equivalent Dose and Safety Margins for the CA-008 Starting Dose

NOAEL (mg/kg)	HED (mg/kg)	HED for CA- 008 HCl ¹ (mg)	HED for free base ¹ (mg)	Proposed Human Clinical Dose (mg)	Safety Margin of FIH Dosing
0.25	0.14	8.4	7.7	0.5	15.4
				1	7.7
				2	3.9
				3	2.6
				4.2	1.8

¹ Based on a 60 kg human

Thus, the safety of CA-008 was established in relevant animal models and is partially based on knowledge from prior human studies with Capsaicin. These results support the potential safety of CA-008 with no apparent abnormal findings. Based on these nonclinical studies, a single instillation administration of CA-008 into the surgical site, at an initial dose of 0.5 mg/person and a maximum dose of 4.2 mg/person, has a minimal risk of causing adverse events. Taken together, the characterization of the pharmacology, pharmacokinetics, and toxicology profiles are considered sufficient to support the intended use of CA-008 in the initial Phase 1 study for the treatment of acute post-surgical pain.

9.5. Selection and Timing of Dose

CA-008 is a pH labile prodrug of capsaicin that rapidly releases capsaicin after administration into tissue. Decision for single administration at the time of surgery is based on capsaicin’s mechanism of action. Capsaicin exposure results in initial excitation followed by a functional desensitization of TRPV-1-expressing nociceptors which continues for some time after removal of capsaicin from the site. Administration while the patient is under anesthesia for the procedure

addresses the pain that results from TRPV1 agonism. Administration of CA-008 during the closure process is ideal for delivering therapy to the surgical site, thus optimizing target engagement. During closure, the surgical tissue is exposed and visible we can ensure that we have complete and adequate delivery of drug to the potential areas where pain is being generated.

What is unknown is whether CA-008 will behave the same as Capsaicin, however we expect that it will. To this end, administration methods that were followed in previous successful post-surgical pain studies will be applied in this 1st in man study.

9.6. **Blinding**

In order to reduce the potential for bias in the study, treatment group assignments will be double-blinded during the study. The subject, investigational site personnel, Sponsor, and Sponsor designees directly involved in the conduct and/or monitoring of this study will not be aware of the treatment group assignments.

Under normal circumstances, the blind will not be broken until all participants have completed treatment. In case of emergency, and only if the information is required by the Investigator to ensure subject's safety in managing a medical condition, the treatment may be unblinded at the site by using a code break module. The code break module will be provided by the Sponsor or designee. If possible, the Investigator should contact the Sponsor prior to unblinding and after any actions have been taken. Whenever a treatment sequence is prematurely unblinded, the reason, date and time of the unblinding, and the individual who broke the blind must be documented. Individual code breaks will result in withdrawal of the participant from the study.

Safety reviews of cohorts of subjects will be performed in a blinded manner unless the data warrant unblinding due to safety concerns. It is assumed that the need to unblind a study subject's treatment assignment will occur in the setting of an SAE, and therefore, all procedures for the reporting of a SAE must be followed (see Section [11.1.3](#)).

9.7. **Prior and Concomitant Therapy**

All non-study medications, including prescription, over-the-counter, or herbal therapies, used by the subject will be documented for the 30 days prior to Screening and throughout the study. The Investigator will determine if the prior/concomitant medication(s) affect the subject's eligibility to participate or continue to participate in the study. The following concomitant medications and therapies may be permitted during the study:

- Rescue medication, as described in Section [9.1.3](#)

On a case-by-case basis, the Investigator is permitted to allow the use of some concomitant medications, for example, to treat an AE, as long as the Investigator determines that the medication will not affect the subject's safety or study integrity (e.g., topical medications). Wherever possible, the Investigator should obtain approval from the Medical Monitor prior to administering the medication.

9.8. **Treatment Compliance**

Because all study medication is being administered by study personnel, no compliance procedures are necessary. Diversion will be monitored and recorded through rescue medication accountability. Any suspected or confirmed diversion will be documented and reported.

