Visit Schedule:	
A. Screening. Subjects will undergo a screening visit up to 28 days prior to surgery; All screening assessments (including ICF) must be completed at least 1 day prior to surgery.
 
B. Study Unit Admission. Day 1 Prior to surgery, subjects will be enrolled and randomized, and baseline evaluations will be performed prior to surgery.
 
C. Day 1 Surgery. Subjects will undergo bunionectomy procedure, and study drug will be infiltrated prior to wound closure. Time 0 will be defined as the time of completion of drug administration.
 
D. Day 1 Post-surgery through 48 hours post-surgery. Subject will remain at the Study Unit site for monitoring and PK assessments.
 
E. Day 2 Safety follow-up and PK assessments
 
F. Day 3 Safety follow-up, PK assessments, and discharge from Study Unit
 
G. Day 8 Clinic visit for study assessments
 
H. Day 15 Clinic visit for study assessments
 
I. Day 29 Clinic visit for study assessments
 
J. Day 36 Clinic visit for wound healing evaluation and Surgical Site assessment (only for subjects who will need a follow up visit after Day 29)
 
Note: For subjects who terminate early, an early termination (ET) visit will be required. Safety and subject-reported outcome assessments will be performed at the ET visit.

Postsurgical Analgesia:	
Day 1 (Hours 0 – 24):
 
 • If needed for management of NPRS score of 4 or higher, oxycodone 5 mg PO q 2 hours prn. 
Day 2 (Hours 25 – 48):
 
 • If needed for management of NPRS score of 4 or higher, oxycodone 5 mg PO q 2 hours prn.

	
Day 3 – Day 15:
 
 • Over-the-counter standard of care analgesics may be used for management of pain. • If needed for management of NPRS score of 4 or higher, oxycodone 5 – 15 mg PO q 4 - 6 hours prn. 
Day 15 (post-visit) – Day 29/ET:
 
 • Over-the-counter standard of care analgesics should be used for management of pain.
--	---

Study Objectives:

Primary:	
To evaluate the safety and tolerability of a single intraoperative administration of CA-008 in subjects undergoing bunionectomy.
 
To evaluate the pharmacokinetics of a single intraoperative administration of CA-008.

Secondary:	To evaluate the efficacy of CA-008 in the management of acute postoperative pain in subjects undergoing bunionectomy.

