8.3. Removal of Subjects from Therapy or Assessment

A subject is free to withdraw his/her consent and discontinue participation in the study at any time for any reason. A subject's participation must therefore be terminated immediately upon his/her request, and the reason(s) for discontinuation appropriately documented.

A subject may be discontinued from the study for any of the following reasons:

- Safety reasons, including AEs or significant concomitant illness, injury, or urgent surgeries/procedures that would, in the judgment of the Investigator, affect assessments of clinical status to a significant extent, require discontinuation of study drug, or both
- At the request of the Sponsor, regulatory agency, or Institutional Review Board (IRB)
- Subject is lost to follow-up
- Subject treatment allocation is unblinded (i.e., individual code break; Section 9.6)
- Death of subject

A subject may also be discontinued from the study, at the discretion of the Investigator and/or Sponsor, for any of the following reasons:

- Subject refuses or is unable to adhere to the study protocol
- Major protocol violation
- Pregnancy
- Use of unacceptable concomitant medication(s)
- It is not considered in the best interest of the subject to continue
- Administrative reasons (e.g., termination of enrollment or study)

The Investigator must maintain a record of all subjects who discontinue from the study prior to completion; the reason(s) for study discontinuation will be documented. In the event that a subject chooses to withdraw from the study, the Investigator should make a reasonable attempt to obtain and record the reason(s) for withdrawal in as much detail as possible, although the subject is not obligated to provide such a reason.

In the event that a subject is discontinued while at the clinical site, the early termination procedures shown in the Schedule of Assessments (Table 1) should be performed prior to discharge from the clinical site. The Investigator should ask the subject to for the Follow-up procedures, provided that the subject has not withdrawn consent for those procedures. If a subject refuses to complete early termination/Follow-up procedures or continued data collection, this information will be recorded.

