13.4.6.1. Adverse Events

Adverse events will be coded by system organ class (SOC) and preferred term using the Medical Dictionary for Regulatory Activities (MedDRA) reporting system. Treatment-emergent AEs are defined as any of the following:

- Non-serious AEs with onset on the date of treatment with the study drug through Day 29 or Early Termination, whichever occurs first;
- Serious AEs with onset on the date of treatment with the study drug through 30 days after Day 29 or Early Termination, whichever occurs first;
- AEs that start before the start of treatment but increase in severity or relationship at the time of or following the start of treatment through Day 29 or Early Termination, whichever occurs first.

The number and percentage of subjects with TEAEs will be displayed for each treatment group by SOC and preferred term. Additionally, TEAEs will be tabulated for each treatment group by severity and by relationship to the study drug. A listing of SAEs will be provided if applicable.

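### Mandatory withdrawal after a code break stops no treatment in this single-dose study, but leaves the remaining scheduled safety visits unsecured, and Protocol and SAP disagree on when adverse-event counting stops

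*Protocol*

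**What the plan says.** **Code break.** Protocol Section 9.6 allows the blind to be broken for an individual in an emergency, when the investigator needs the allocation to manage the subject safely. It then says: "Individual code breaks will result in withdrawal of the participant from the study". It goes on to assume that the need to unblind a subject's "treatment assignment will occur in the setting of an SAE".

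**Discontinuation.** Section 8.3 puts an individual code break in a list that opens with "A subject may be discontinued from the study for any of the following reasons", and refers back to Section 9.6. For a subject discontinued while at the site, "early termination procedures shown in the Schedule of Assessments (Table 1) should be performed prior to discharge from the clinical site". The next sentence reads: "The Investigator should ask the subject to for the Follow-up procedures, provided that the subject has not withdrawn consent for those procedures". Its verb is missing.

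**What continues.** The synopsis says: "For subjects who terminate early, an early termination (ET) visit will be required". Section 7.1.8 lists the content of the Day 29/ET visit, including surgical site, neurosensory and physical examinations, vital signs and X-ray. Sections 10.5.9 and 11.1.2 follow serious and possibly related events until they resolve or stabilise. Section 11.1.3.1 keeps all SAEs reportable within 24 hours for 21 days after ET, and possibly related ones after that.

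**Counting.** Protocol Section 13.4.6.1 counts as treatment-emergent "Non-serious AEs with onset on the date of treatment with the study drug through Day 29 or Early Termination, whichever occurs first". Its serious-event window runs 30 days beyond the same cut-off. SAP Section 8.2 uses Day 29 for non-serious and Day 59 for serious events and does not mention ET.

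**The concern.** Withdrawal after unblinding can have a purpose where dosing continues. Here each subject receives one intraoperative administration, so once surgery is over the rule has no treatment to stop. What it puts at risk is observation, in a first-in-human study with safety as a primary objective.

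By the Protocol's own assumption, the subjects affected tend to be those with a serious event, so any loss of follow-up depends on the outcome. The provisions that survive withdrawal mainly track events already found. The scheduled Day 8, 15 and 29 examinations are what would detect new wound or neurosensory findings, and the Day 29 wound assessment decides whether Day 36 takes place. If these visits lapse, the subject stays in the denominator and is counted as having had no further events.

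**Working it through.** The plan gives no figure to reproduce: the sample size is not statistically based, and no code-break rate is stated. The check is a reading of the sections together, with simple arithmetic.

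**1. What secures each later observation after a code break?**

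| Observation | Provision | Status |
|---|---|---|
| Safety assessments at withdrawal | Synopsis; Sections 7.1.8, 8.3 | Required |
| Course of an SAE or possibly related AE | Sections 10.5.9, 11.1.2 | Required |
| New SAE within 21 days after ET | Section 11.1.3.1 | Reportable if it becomes known |
| Remaining Day 8, 15 and 29 visits | Section 8.3 | A request, in an incomplete sentence that follows the in-clinic case |
| Day 36 | Sections 7.1.8, 10.5.7 | Depends on Day 29 taking place |

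Two other passages might seem to fill the gap. The continued safety follow-up in Section 9.1.3 is written for subjects who leave the efficacy portion because of inadequate analgesia. The consent to continued data collection in Section 13.4.5.1 (SAP Section 7.1) stands under missing efficacy data and refers to stopping study medication, which cannot happen after a single dose. Neither clearly covers a code break.

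**2. How far apart are the counting windows?** Let ET fall on Day d. I read the Protocol's serious-event window as 30 days after the earlier of Day 29 and ET.

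- Non-serious window: closes on Day d in the Protocol, a loss of 29 − d days against the SAP.
- Serious window: closes on Day d + 30 in the Protocol, against 29 + 30 = Day 59 in the SAP.
- 24-hour reporting of all SAEs: ends on Day d + 21, against 29 + 14 = Day 43 for a subject who completes Day 29.

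| ET day | Non-serious days lost | Serious window ends (SAP: 59) | SAE reporting ends (completer: 43) |
|---|---|---|---|
| 3 | 26 | 33 | 24 |
| 8 | 21 | 38 | 29 |
| 15 | 14 | 45 | 36 |

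**3. What could one lost subject do to a dose group?** Each cohort has 6 active subjects, so one is 1/6 = 16.7%. Assume complete loss of later follow-up, independent subjects and a common late-event rate p. The chance of seeing at least one late event is 1 − (1 − p)^n:

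| Assumed p | n = 6 | n = 5 |
|---|---|---|
| 5% | 0.265 | 0.226 |
| 10% | 0.469 | 0.410 |
| 20% | 0.738 | 0.672 |
| 30% | 0.882 | 0.832 |

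Because the denominator stays at 6, the expected reported incidence of such an event is 5p/6. At p = 20% that is 5 × 0.20 / 6 = 16.7% in place of 20%. The rates are illustrative; the documents give none.

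**The case against.** The strongest reply is that withdrawal is not the end of safety follow-up. A reader of Section 9.6 alone might infer that it is, or that a code break on Day 2 forfeits every later visit. The documents do not support either reading. The ET visit is required, serious and possibly related events are followed to an outcome, and Section 8.3 tells the investigator to ask for the follow-up procedures. In Table 1, Follow-Up is the heading over the Day 8 to Day 36 columns, and a Day 2 break is an in-clinic discontinuation, the case which that paragraph addresses. This part of the reply stands.

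A reader might also infer that the rule removes exactly the subjects who have a serious event. That goes too far. Section 9.6 states an assumption about when unblinding will be needed; it does not say that every SAE leads to a code break.

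It can further be said that Sections 8.3 and 9.6 do not truly conflict. Only the second list in Section 8.3 is expressly discretionary, and the code-break entry in the first list points to Section 9.6. This is a fair reading, and the difference between may and will is the weaker part of the point. The tension that remains is between withdrawing a subject from the study and asking the same subject to attend its visits.

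Lastly, the SAP documents the final analysis, and its TEAE window already has no ET cut. That limits the counting problem but does not remove it. The Protocol says otherwise, SAP Section 12 does not list the change, and an open window counts nothing unless someone still sees the subject.

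**Conclusion.** The point holds in a limited form. Section 9.6 imposes a withdrawal that has no treatment purpose in a single-dose study, and no provision firmly secures the remaining scheduled safety assessments. Separately, the Protocol and SAP define the TEAE window differently, by 26 days for ET on Day 3 and 14 days for ET on Day 15.

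The effect is confined to new events after the withdrawal. The subject remains in the Safety Population, and the event behind the code break is still counted. Any downward bias therefore lies in the incidence of particular later findings, such as wound or neurosensory changes, and not in the triggering event. The 16.7% of a dose group is an upper bound: it assumes one code break in an active subject and no later attendance. The documents give neither a code-break rate nor an expected refusal rate, so the likely size cannot be stated. The change is still worth making, because dose groups are small and the visits are already planned.

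**What to change.** 1. **Section 9.6.** Replace the withdrawal sentence with wording such as: *A subject whose treatment code is broken remains in the study for all remaining scheduled safety assessments through Day 29, and Day 36 if required, unless consent is withdrawn. Efficacy data collected after the code break will be flagged.*
2. **Section 8.3.** Bring the code-break entry into line with this. Complete the follow-up sentence so that it names the visits and applies after discharge as well as in the clinic.
3. **Section 13.4.6.1.** Remove the ET cut from the TEAE definitions so that they match SAP Section 8.2: Day 29 for non-serious and Day 59 for serious events.
4. **SAP.** Add one sentence on how flagged NPRS scores after a code break enter the AUC analyses, since Section 7.1 currently imputes scores for subjects who drop out before Day 15. Record any remaining departure from the Protocol in Section 12.

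The cost is a few sentences in a protocol amendment, with the IRB approval described in Section 14.6, and one or two sentences in the SAP. No new visits or procedures are needed.
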